### **Eligibility criteria for public schools**

#### **Inclusion criteria**

- Schools that have functional facilities of WASH will be selected.
- Single-gender schools will be selected
- Schools that will give informed consent to participate in the study

#### **Exclusion criteria**

[figure not shown]
- Schools having a public-private partnership
- School runs by NGO
- School already participating in any other research program

**This study will be conducted in three phases.**

I. Form active phase

II. RCT phase

III. Dissemination phase

**Detail of project activities**

Outline of the study
Formative Phase

Activities	Strategies	Target Population	Channels	Material
Formative assessment qualitative	Focus group discussions (FGDs)	
 
• Adolescents (6,7,8 grade)
 
• Teachers
 
• Mothers/immediate caretakers
 
	Researcher	FGD interview guide
	Key informant interview (KII)	School management	Researcher	Interview guide
	School document analysis	
 
• Curriculum of 6,7,8 grade
 
• School policy
 
	Researcher with teachers	Reviewing school curriculum, textbooks, and policy
RCT Phase				
Baseline assessment	Knowledge, attitude, and practices (KAP) assessment	Early school adolescents (6,7,8 grade)	Researcher	KAP survey questionnaire
	Anthropometric measurement (BMI)	Early school adolescents (6,7,8 grade)	Researcher	-Height scale -weight machine -WHO growth chart
	Micronutrient assessment (complete blood picture, Zinc and serum calcium, Vitamin D)	Adolescents sample (subset of 108 participants, 54 from each group)	LAB (AKU)	A blood test from Lab
	Physical assessment (skin, hair, eyes, nail, tongue, teeth, gums,)	Early school adolescents (6,7,8 grade)	Researcher	Check list
	Observation (Eating and WASH practices) at school	Early school adolescents (6,7,8 grade)	Researcher	Observation checklist
Intervention phase (Duration 4 months)				

Module development	Development of module on Nutrition and WASH component	For early adolescents (6,7,8 grade)	
 
• Research team
 
• Nutritionist
 
	
 
• Pakistan Dietary guideline
 
• WHO guidelines
 
• UNICEF guidelines
 
• Literature search
 

Workshop	2 workshops will be conducted for the school teachers	For School teachers (Teaching 6,7,8 grade)	Researcher	Based on the Module & teaching strategies
Deworming	Administering Deworming medicine to study participants	Early adolescents (6,7,8 grade)	School teachers	Tab Zentel
	Micronutrient supplementation to study participants	Early adolescents (6,7,8 grade)	School teachers	Micronutrient supplementation 1 tab daily for three months
Healthy diet education	
 
• Health education session
 
• Role play
 
• Quiz and games
 
• Flip charts
 
• Log books for food intake
 
• Peer education through a group presentation
 
• Incentive for healthy lunch
 
	Early school adolescents (6,7,8 grade)	School teachers	
 
• Module on Healthy diet
 
• 30-45 min session on nutrition on a weekly basis for 12 weeks
 
• Poster and Charts
 
• Flip charts with key messages
 

	
 
• Take-home cooking recipes based on local context and food available
 
	Mother/immediate care taker	
 
• Through adolescent (6,7,8, grade)
 
	
 
• Diary/log books
 

Water, Sanitation, and Hygiene (WASH)	
 
• Showing video on steps of hand washing
 
• Demonstration of hand washing technique
 
• Take home handout
 
	Early school adolescents (6,7,8 grade)	
 
• School teachers
 
	
 
• Module on WASH
 
• 30-45 min session on WASH on weekly basis for 4 weeks
 
• Charts and posters
 

The proposed intervention will be finalized after formative assessment (FGDs with teachers and mothers and KI with school management).

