**b. Dependent variables/Outcome of study**

1. Body Mass Index: All school going 6- 8 grade adolescents will undergo anthropometric measurements such as height, and weight (BMI). The measurement will be taken at baseline and end line by using WHO standard growth chart.
2. Micronutrients: Blood sample will be collected twice (baseline and end line) from a subset of 108 adolescents (54 intervention group,54 control group). The blood samples will help to assess the impact of intervention on micronutrient deficiencies (Iron, Zinc, Calcium, CBC, Vitamin D)
3. Physical examination: Physical examination like hair, skin, nail, eye (bitot spot), mouth (dental caries), and goiter will be assessed for micronutrient deficiencies at baseline and end line.
4. Knowledge, attitude, and practices regarding nutrition and WASH: a structured questionnaire will be used to collect data on nutrition and WASH-related indicators. The survey will be administered at baseline and end line. The indicator assessed will be adolescent health status and knowledge, attitude, and practices regarding nutrition and WASH practices.

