### **Secondary objective**

To measure the impact of school-based nutrition education and water, sanitation, and hygiene intervention on micronutrient levels among early adolescents.

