**Post-intervention phase (Duration 2 months)**

End line Assessment	KAP survey	Early school adolescents (6,7,8 grade)	Researcher	KAP survey questionnaire
	Anthropometric measurement (BMI)	Early school adolescents (6,7,8 grade)	Researcher	
 
• Height scale
 
• Weight machine
 
• WHO growth chart
 

	Micronutrient assessment (Blood complete picture, Zinc and Calcium)	30 % of the total Adolescents sample (108 participants, 54 from each group)	LAB (Aga Khan Lab)	Blood test from Lab
	Physical assessment (skin, hair, eyes, nail, tongue, teeth, gums,)	Early school adolescents (6,7,8 grade)	Researcher	Checklist
	Observation (Eating and WASH practices) at School	Early school adolescents (6,7,8 grade)	Researcher	Observation Checklist
Dissemination Phase				
	Research uptake	Stakeholders (adolescents, mother/immediate caretakers, school teachers, school management. community stakeholder	Research team	Health mela, health screening, publication

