### **Sample Size & Sampling Strategy**

The sample size was calculated by using PASS software. Sample sizes were estimated to change in nutritional status of early adolescent boys and girls. A sample size of 360 adolescents

(180 in each intervention and control group) will achieve 80% power assuming 42% malnutrition among students in the control arm and at least 6% reduction in the intervention arm having 90 students from each school at a two-sided 5% level of significance.

To assess the micronutrient levels (Iron, Zinc, Calcium, CBC, and Vitamin D) through a blood sample, a subset of 108 adolescents 6-8 grade school going adolescents (54 intervention group, 54 control group) from this total sample size (360) will be selected through random selection.

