### **Activities of baseline assessment**

Activities	Purpose	Frequency
KAP survey	To know the KAP regarding nutrition and WASH	Baseline and end line
Anthropometric measurements	To identify the number of thin, underweight, Overweight, and Obese adolescents in 6-8 grade	Baseline and end line
Physical assessment	To identify the health status of adolescents	Baseline and end line

Monitoring CBC, Zinc, Calcium, and Vitamin D level	To identify the deficiency of micronutrients at baseline and improvement at the end line	Baseline & end line
Observations	To assess the practices related to major determinants of malnutrition i.e. nutrition, water, sanitation, and hygiene.	Baseline & end line

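### Serum calcium is insensitive to calcium intake, so it cannot show calcium deficiency or its improvement

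*Protocol*

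**What the plan says.** All references are to the protocol.

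- **Detail of project activities**, baseline row: "Micronutrient assessment (complete blood picture, Zinc and serum calcium, Vitamin D". This is the only place that specifies serum.
- **Post-intervention phase**, end-line row: "Micronutrient assessment (Blood complete picture, Zinc and Calcium". Calcium is measured again by a laboratory blood test; vitamin D is not in this row.
- **Activities of baseline assessment**: the entry "Monitoring CBC, Zinc, Calcium, and Vitamin D level" carries the purpose "To identify the deficiency of micronutrients at baseline and improvement at the end line", with measurement at both time points.
- **b. Dependent variables/Outcome of study**: "The blood samples will help to assess the impact of intervention on micronutrient deficiencies (Iron, Zinc, Calcium, CBC, Vitamin D".
- **Secondary objective**: the effect of the "intervention on micronutrient levels among early adolescents".
- **Sample Size & Sampling Strategy** (RCT phase): the blood tests are done in "a subset of 108 adolescents 6-8 grade school going adolescents (54 intervention group, 54 control group".

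No other measure of calcium status is named as an outcome. The protocol gives no cut-off for low calcium and does not say whether total, albumin-corrected or ionised calcium is meant. It also does not say whether the daily tablet contains calcium.

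**The concern.** The protocol asks the calcium test two questions: which pupils are deficient at baseline, and whether the intervention improves this. The Introduction raises calcium as a nutritional matter, namely greater intake needs during skeletal growth. Serum calcium does not track intake. The body defends the circulating level and draws on bone to do so, so a pupil with a poor intake will usually have a normal value, and a better diet will usually not raise it.

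Two conclusions are then at risk: that calcium nutrition is adequate because baseline values are normal, and that the package does nothing for it because the arms look alike at end line. Neither follows from this test. The protocol plans to share its findings with national nutrition programme managers and policymakers, so an unsupported statement on calcium could carry beyond the trial.

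**Working it through.** **Subset size.** The end-line row gives the blood subset as 30% of the total sample, and the total is 360. 0.30 × 360 = 108, and 54 + 54 = 108, so the stated figure reproduces. (The Introduction gives 180 for the subset. That is a separate inconsistency and does not bear on this point.)

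**Is there a calcium calculation to check?** No. The protocol states no effect size, standard deviation, cut-off or power for calcium. The rest is a comparison of purpose with measurement.

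**Premise from outside the documents.** Serum calcium is held in a narrow range by hormonal control, with bone as the reserve. This is general physiology, stated here as an assumption; no figure is taken from it.

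| Intended reading | What the protocol relies on | Does it follow? |
|---|---|---|
| Calcium deficiency at baseline | A blood calcium value | No. A normal value is compatible with low intake. |
| Improvement at end line | Change in that value | No. Intake can improve while the value stays the same. |
| Impact of the intervention on deficiency | Comparison of arms on that value | No. Similar arms do not show absence of effect. A difference could come from vitamin D status or albumin. |

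**Could another listed measure supply the answer?**

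- Vitamin D is not a measure of calcium intake or calcium status. It is also missing from the end-line row and from the Baseline assessment paragraph, although the outcome section and the activities list include it.
- The Data collection tool/instrument section describes 24 nutrition questions without listing them. Whether any concerns calcium-rich foods cannot be told from the protocol.

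**Why no power figure is given.** It would need an assumed frequency of low serum calcium and an assumed response of serum calcium to intake. The documents give neither. It would also need a cut-off, whereas the Data analysis plan assigns a t-test to continuous variables. The argument does not need it: a marker that does not reflect intake does not answer the question at any sample size.

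**The case against.** The strongest reply has three parts.

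1. The secondary objective speaks of levels, and a serum calcium concentration is a level. The protocol never says that the test measures intake or bone calcium, and the Introduction's remark on skeletal growth is background, made about boys. This stands as far as it goes: reporting serum calcium as a level is legitimate. It does not cover the outcome section or the activities list, both of which use the panel, with calcium named in it, to judge deficiency.
2. The stated purpose belongs to the panel as a whole, and calcium is one analyte in it. That is correct and limits the weight of the point. It does not make calcium fit for that purpose.
3. A reader might infer that the trial is bound to find calcium adequate and the intervention ineffective on it. The documents do not support that. Serum calcium can fall in marked vitamin D deficiency, total calcium shifts with albumin, and a chance or school-level difference could reach significance. With no cut-off stated, the protocol nowhere commits itself to declaring calcium adequate. The claim made here is only that the value, changed or unchanged, cannot carry the interpretation assigned to it.

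**Conclusion.** The point holds as a limit on interpretation. The protocol uses serum calcium to identify calcium deficiency and its improvement, and nothing in the document addresses the test's insensitivity to intake.

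Its reach is small: one of the five entries in the outcome list (iron, zinc, calcium, CBC, vitamin D), under the secondary objective, in the blood subset. The primary objective and the other analytes are untouched. No numerical bias or loss of power can be derived from the documents. The conclusion rests on the physiological premise above, and on reading the end-line calcium test as the same test as at baseline, which the shared entry in the activities list supports.

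**What to change.** - In **b. Dependent variables/Outcome of study** and **Activities of baseline assessment**, remove calcium from the markers used to judge micronutrient deficiency and its improvement.
- Make the other calcium entries consistent with this: the RCT-phase paragraph of the Introduction, the baseline row of Detail of project activities, the end-line row of the Post-intervention phase table, the Baseline assessment paragraph, and Sample Size & Sampling Strategy.
- Keep the serum calcium already drawn as a descriptive result only. State that no conclusion on calcium deficiency, or on the intervention's effect on calcium nutrition, will be drawn from it.
- Do not substitute vitamin D as a calcium marker.
- If the existing questionnaire contains items on calcium-rich foods, report the answers as reported intake and not as deficiency. If it contains none, make no calcium statement from it.

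The cost is protocol wording, with no new sample, test or visit. The trial gives up a blood-based claim on calcium, and may have nothing to say on calcium nutrition if the questionnaire lacks such items.

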**Post-intervention phase (Duration 2 months)**

End line Assessment	KAP survey	Early school adolescents (6,7,8 grade)	Researcher	KAP survey questionnaire
	Anthropometric measurement (BMI)	Early school adolescents (6,7,8 grade)	Researcher	
 
• Height scale
 
• Weight machine
 
• WHO growth chart
 

	Micronutrient assessment (Blood complete picture, Zinc and Calcium)	30 % of the total Adolescents sample (108 participants, 54 from each group)	LAB (Aga Khan Lab)	Blood test from Lab
	Physical assessment (skin, hair, eyes, nail, tongue, teeth, gums,)	Early school adolescents (6,7,8 grade)	Researcher	Checklist
	Observation (Eating and WASH practices) at School	Early school adolescents (6,7,8 grade)	Researcher	Observation Checklist
Dissemination Phase				
	Research uptake	Stakeholders (adolescents, mother/immediate caretakers, school teachers, school management. community stakeholder	Research team	Health mela, health screening, publication

### **Phase I: Formative phase**

This phase aims to develop a module on Nutrition and WASH components. This phase consists of FGD with adolescents, their mothers/ immediate caretakers, and school teachers. Key informant interviews will also be conducted with school management. Furthermore, the school curriculum and textbooks for 6-8 grade will also be analyzed.

### **Research Questions**

**For school adolescents**

1. What is the perception of 6-8 grade school going early adolescents regarding nutrition?
2. What is the perception of 6-8 grade school going early adolescents regarding Water, Sanitation, and Hygiene?
3. What areas/topics do 6-8 grade adolescents like to learn regarding nutrition and WASH?

**For School Teachers**

1. What is the perception of school teachers regarding adolescents' nutrition?
2. What is the perception of school teachers regarding water, sanitation, and hand-washing practices at school?
3. What is the perception of school teachers regarding the nutritional status of school-going adolescents?
4. What are the teacher's recommendations that how nutrition education and WASH can be built into school programs?

**For Mothers/immediate Caretakers**

1. What is the perception of mothers/immediate caretakers of 6-8 grade school-going adolescents regarding nutrition?
2. What is the perception of mothers/immediate caretakers of 6-8 grade adolescents regarding water, sanitation, and handwashing awareness at five critical times?
3. What are the challenges mothers/immediate caretaker face in fulfilling the nutritional requirement of their adolescents?

**Participants**

Participants will be;

- Early Adolescents (6,7,8 grade students)
- School teachers teaching nutrition-related subjects in 6-8 grade adolescents

- Mother/ immediate caretaker of adolescents
- School management (head teacher/principal)

### **Eligibility criteria for adolescents**

#### **Inclusion Criteria**

- Students studying in 6, 7, and 8 grades
- Informed consent given by adolescent's mothers/immediate caretakers
- Assent was given by the adolescent

### **Eligibility criteria for teachers**

#### **Inclusion criteria**

- School teachers currently teaching nutrition-related subjects to 6,7, and 8-grade students
- School teachers who will give consent to be part of this study

### **Eligibility criteria for mothers/immediate caretakers**

#### **Inclusion criteria**

- Mothers/ immediate caretakers of adolescents studying in 6, 7, and 8 grades
- Mothers/ immediate caretakers who will give informed consent

### **Sample Size & Sampling Strategy**

A purposive sampling technique will be used for the inclusion of the participants. The study participant (adolescents, their mothers/immediate caretakers, and school teachers) will be included in the study from four public schools (2 boys and 2 girls) from Gojra for the FGD. The adolescents, their mothers/immediate caretakers, and teachers will be selected with the help of the school management or Headteacher/school principal. The number of FGDs is 1-2 for each group in this study and will include 8-12 participants. For the key informant interview, the school management from four selected schools will be invited.

### Activities of the Formative Phase

Activities	Target population	Purpose
Focus group discussions	
 
• Adolescents
 
• Mothers/immediate care taker
 
• School teachers
 
	
Explore the perception of adolescents regarding nutrition and WASH.
 
Explore their perception of what role school can play to promote healthy diets and WASH practices among adolescents. Their opinion will also be sought to devise strategies for improving dietary and WASH practices.

Key Informant interviews	School management	To explore enablers and barriers to school-based interventions to improve knowledge, attitude and practices related to nutrition and WASH practices among school adolescents.

**School document analysis:** Components of a healthy diet, and personal and environmental hygiene will be assessed in the 6-8 grade school curriculum (6-8 grade textbook). School policy will also be reviewed for the integration of nutrition and hygiene components.

### Validity and reliability

#### Qualitative tool

For FGD, an interview guide will be used. For validation 1-2 interview will be held before identifying the issue that might the respondents face in the interpretation of questions. In the present study, the rigor of the qualitative method will be maintained by using Lincoln and Cuba's (1985) criteria. Trustworthiness of research will be maintained by making the data credible, dependable, transferable, and confirmable (Pandey, (2014). To make the study credible and dependable, following measures will be taken; an interview will be conducted until the

achievement of the saturation. Secondly, detailed information will be provided to the readers about all aspects of the study from design to data analysis, so that readers can understand the study in detail. This will help the reader to monitor whether research practices have been followed in true letter and spirit or not. Prior to the start of the data collection element, the researcher will write and review the reflection, so that the influence of his/ her values will be minimized. Moreover, a thorough discussion will be a continuous part till the finalization of the themes, categories and codes, which will be used for this study.

### **Data collection process**

The principal investigator will collect data. Initially, a meeting with the school principal and teachers will be done to share the overall scope and objectives of the study and to seek for their cooperation throughout the study. Informed consent will be taken from school teachers and mothers/ immediate care takers of 6-8 grade school going adolescents. Secondly, to approach 6, 7, and 8 grade adolescents, informed consent will be first taken from their mothers or immediate caretaker and school management. Also, a written informed assent will be taken from the adolescents available in Urdu and English or local language. Study participants will be briefed about the purpose of the study and assured of anonymity and confidentiality of the information shared. In case, participants have any queries related to the discussion, an explanation will be provided to them.

Focus group discussion (FDGs) with school adolescents, school teachers, and mothers/ immediate caretakers will be conducted with the help of an interview guide. Adolescents (12-16 adolescents

(two-three from each class) will be invited for FDGs with the help of the school management.

12 -16 mothers / immediate caretakers of 6- 8 grade school-going adolescents will be invited for 1-2 FDGs in a school setting. The mothers/ immediate caretakers will be selected with the help

of the school management from intervention and control schools. Also, two to three school teachers from each intervention and control school will be invited for FDGs. All FDGs will be conducted in a separate, quiet, well-lit room in school setting for about 45 minutes to 60 minutes. FDGs will be carried out till the point of saturation. In addition, all four schools (control and intervention) head teachers/principals will be interviewed. Interview will last about 30 minutes and will be conducted with the help of an interview guide.

### **Data analysis plan**

#### **Qualitative data**

Content analysis will be checked through the Creswell framework (Creswell, 2013). This framework consists of five stages. First of all, in the organization of data the text will be transcribed into local language and after that will be translated into English. After that, the code number will be allocated to each transcript. The second step is reading and memorizing in which text will be read several times to develop an in-depth understanding of the data. Data description, classification, and interpretation into themes and codes comprise third step of this framework. For the present study, codes, categories, and themes will be developed as described by Creswell. The fourth step is interpreting the data, where the finding of the study will be compared with the existing literature to verify and identify new findings. Data will be represented and visualized into tabular and figure forms for comprehension.

